## 8. OTHER ASSESSMENTS

### 8.1 MMSE

For MMSE in subjects with AD, change from baseline for pooled treatment allocation will be analyzed using a restricted maximum likelihood based repeated measures linear mixed model. The model will include fixed effects for AChEI/Memantine use as randomized in the prior study (Yes and No), time since baseline in the prior study (continuous), AChEI/Memantine use as randomized in the prior study by time interaction and the prior study baseline MMSE, prior study (015 and 005) and region (The Americas and RoW). In addition, the baseline MMSE from the prior study will be included as a covariate. An unstructured covariance model will be used. The Kenward and Roger method of calculating the denominator degrees of freedom will be used for the tests of fixed effects. Annualized LS means will be provided. Additionally, observed means according to the visit windowing in [Appendix A](#) will be provided.

If more than 20 bvFTD subjects have MMSE values in 020, the above analysis will be repeated for bvFTD subjects.

If more than 10 subjects with AD discontinue AChEI/Memantine in 020, then summary of MMSE at the visits prior to and the visits subsequent to discontinuation will be provided.

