## **4. GENERAL ANALYSIS CONSIDERATIONS**

The Safety population will include all subjects who take at least one dose of study drug. All analyses described in this SAP will be based on the Safety Population. All subjects entering the study, even if not known to have taken a dose, will be accounted for in a listing.

The statistical analyses will be reported using summary tables, figures, and data listings. Continuous variables will be summarized with means, standard deviations, medians, minimums, and maximums. Categorical variables will be summarized by counts and by percentage of subjects in corresponding categories.

For purposes of calculations of change from baseline, Baseline (Visit 1) for the open-label study will be used. Depending on the parameter, the data may have been acquired during the double-blind study of prior participation.

Summary tables will present results by diagnosis (AD or bvFTD) and an “All Subjects” column.

Individual subject data obtained from the CRFs (including mapped data), central clinical laboratory (local laboratory results are entered on the CRFs), and any derived data will be presented by subject in data listings. Listings will include relative study day, where negative values will indicate visits prior to first dose of study drug in 020, and any data collected after discontinuation of study drug will be flagged as follow-up. All data captured on the CRF, including specific descriptions of ‘other’ and comments fields, will be included on the listings. Listings will be sorted by subject number.

All analyses and tabulations will be performed using SAS® Version 9.4 or higher. Tables, listings, and figures will be presented in RTF format. Upon completion, all SAS® programs will be validated by an independent programmer. In addition, all program output will undergo a senior level statistical review. The validation process will be used to confirm that statistically valid methods have been implemented and that all data manipulations and calculations are accurate. Checks will be made to ensure accuracy, consistency with this plan, consistency within tables, and consistency between tables and corresponding data listings. Upon completion of validation and quality review procedures, all documentation will be collected and filed by the project statistician or designee.

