## Appendix F: List of Tables, Figures and Listings

### List of Tables

Table Number	Table Description
14.1.1.1	Subject Disposition (All Subjects)
14.1.1.2	Subject Disposition by Region (All Subjects)
14.1.1.3	Subject Disposition by Country and Site (All Subjects)
14.1.1.4	Subject Disposition – Non-AChEI/Memantine Users (All Subjects)
14.1.2.1	Study Discontinuation by Time Period (Safety Population)
14.1.2.2	Study Discontinuation by Time Period – Non-AChEI/Memantine Users (Safety Population)
14.1.2.3	Study Discontinuation by Time Period and by Region (Safety Population)
14.1.3.1	Protocol Deviations (Safety Population)
14.1.3.2	Protocol Deviations by Critical, Major and Minor Categories (Safety Population)
14.1.4.1	Demographic and Baseline Characteristics (Safety Population)
14.1.4.2	Demographic and Baseline Characteristics – Non-AChEI/Memantine Users (Safety Population)
14.1.5.1	Medical History (Safety Population)
14.1.5.2	Medical History – Non-AChEI/Memantine Users (Safety Population)
14.1.6.1.1	Concomitant Medications Ongoing On Day 1 of Dosing (Pre-existing Medications) (Safety Population)
14.1.6.1.2	Concomitant Medications Ongoing On Day 1 of Dosing (Pre-existing Medications) – Non-AChEI/Memantine Users (Safety Population)
14.1.6.2.1	Concomitant Medications that Started On or After Day 1 of Dosing (Study-emergent Medications) (Safety Population)
14.1.6.2.2	Concomitant Medications that Started On or After Day 1 of Dosing (Study-emergent Medications) – Non-AChEI/Memantine Users (Safety Population)
14.1.6.3.1	Concomitant Medications (Pre-existing and Study-emergent Medications) (Safety Population)
14.1.6.3.2	Concomitant Medications (Pre-existing and Study-emergent Medications) – Non-AChEI/Memantine Users (Safety Population)
14.2.1.1	MMSE (Safety Population: Subjects with AD)

Table Number	Table Description
14.2.1.2	MMSE Annualized LS Means (Safety Population: Subjects with AD)
14.2.2	RUD Lite (Safety Population: Subjects with at Least One Post-Baseline RUD Lite Questionnaire)
14.2.3	EQ-5D-5L (Safety Population: Subjects with at Least One Post-Baseline EQ-5D-5L Questionnaire)
14.3.1.1	Study Drug Exposure and Compliance (Safety Population)
14.3.1.2	Study Drug Exposure and Compliance – Non-AChEI/Memantine Users (Safety Population)
14.3.2.1.1.1	Overall Summary of Adverse Events Ongoing On Day 1 of Dosing (Pre-existing Adverse Events) (Safety Population)

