**Table 14.2.1.2**  
**MMSE Annualized LS Means**  
**Safety Population**

Time Point	AD (N= )
Baseline 	
n	n
Mean (SD)	xx.x (xx.xx)
Median	xx.x
Min, Max	xx, xx
52 Weeks	
LS Mean 	xx.x
95% CI 	(xx, xx)
104 Weeks	
LS Mean 	xx.x
95% CI 	(xx, xx)
.	
.	
.	

 Baseline is defined as the last non-missing value prior to first dose of study drug in the prior study.

 LS means and 95% CIs are from a restricted maximum likelihood based repeated measures linear mixed model with fixed effects for AChEI/Memantine use as randomized in the prior study (Yes and No), time since baseline in the prior study (continuous), AChEI/Memantine use as randomized in the prior study by time interaction and the prior study baseline MMSE, prior study (015 and 005) and region (The Americas and RoW). In addition, the baseline MMSE was included as a covariate. An unstructured covariance model was used.

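### The MMSE model lets AChEI/memantine users and non-users decline at different rates, but Table 14.2.1.2 reports one AD LS mean and 95% CI per year, with no results by use and no stated weights

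*SAP*

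**What the plan says.** SAP 8.1 opens: "For MMSE in subjects with AD, change from baseline for pooled treatment allocation will be analyzed". The model is a REML repeated-measures mixed model. Its fixed effects are AChEI/memantine use (Yes/No, as randomized in the prior study), time since the prior-study baseline as a continuous term, "AChEI/Memantine use as randomized in the prior study by time interaction", prior-study baseline MMSE, prior study (015 or 005) and region (the Americas or the rest of the world). On output, SAP 8.1 says "Annualized LS means will be provided" and adds that observed means by visit window will be given.

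The shell of Table 14.2.1.2 (SAP Appendix G) has one column, AD, with one LS mean and one 95% CI at 52 weeks, at 104 weeks and so on. Its footnote begins "LS means and 95% CIs are from a restricted maximum likelihood based repeated measures linear mixed model" and goes on to restate the model terms. It gives no weights.

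SAP section 4 fixes the software ("All analyses and tabulations will be performed using SAS") but no option or contrast. Appendix F repeats many tables for non-users of AChEI/memantine, including disposition, exposure, adverse events, laboratory results and vital signs. It lists no such repeat for the MMSE tables.

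**The concern.** Once use interacts with time, the model has two AD trajectories. A single AD mean at a given year exists only after weights for the two groups are chosen, and the SAP chooses none. Under the conventional equal weighting, the table cell would have the same expected value whether non-users were 10% or 50% of the subjects. A reader would take it as the average decline of the AD subjects in this study, and its 95% CI as an interval for that average. Prior study and region leave the same question open.

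The shell also omits what the interaction was put in to estimate, namely the two slopes. Table 14.2.1.2 is the only table shell in the SAP with a confidence interval, so its figures are likely to be quoted.

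**Working it through.** The plan states no LS mean, user share or weight, and Protocol 9.2 says sample size calculation does not apply. There is therefore no figure to reproduce. The check compares two ways of averaging the same fitted model.

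**Set-up.** Let q be the non-user share among the AD subjects analysed, and mU(t) and mN(t) the model means for users and non-users at time t.

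- Equal weight: 0.5 mU(t) + 0.5 mN(t)
- Subject weight: (1 - q) mU(t) + q mN(t)
- Subject weight minus equal weight: (q - 0.5) x [mN(t) - mU(t)]

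The bracket includes any main effect of use as well as the slope difference. The discrepancy is zero if q = 0.5 or the group means are equal at t.

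**Standard error.** If both groups have the same per-subject variance, the ratio of equal-weight to subject-weight SE is 0.5 / sqrt(q(1 - q)).

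**Illustration.** Both q and the slope gap are assumptions, and the main effect of use is set to zero. The absolute discrepancy is then |q - 0.5| x gap x years.

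| q | Gap (points/year) | 52 weeks | 104 weeks | SE ratio |
|---|---|---|---|---|
| 0.40 | 0.5 | 0.1 x 0.5 = 0.05 | 0.10 | 1.02 |
| 0.30 | 1 | 0.2 x 1 = 0.20 | 0.40 | 1.09 |
| 0.15 | 2 | 0.35 x 2 = 0.70 | 1.40 | 1.40 |
| 0.10 | 2 | 0.4 x 2 = 0.80 | 1.60 | 1.67 |

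For scale, Protocol 8.1 cites a typical AD decline of 2-4 MMSE points over 12 months. Take the ends of that range as the two slopes, with users at -4 and non-users at -2 (the direction is also an assumption). The equal-weight value is 0.5(-4) + 0.5(-2) = -3.0 at 52 weeks and -6.0 at 104 weeks for every q. The subject-weighted value at q = 0.15 is 0.85(-4) + 0.15(-2) = -3.7, and -7.4 at 104 weeks.

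**Simulated check.** One REML fit used 1000 simulated subjects, 84.6% of them users, with true slopes of -4 and -2, random intercepts and slopes, and baseline, study and region terms.

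| | 52 weeks (95% CI) | 104 weeks (95% CI) |
|---|---|---|
| Equal weight | -2.92 (-3.15 to -2.68) | -5.85 (-6.19 to -5.51) |
| Subject weight | -3.76 (-3.93 to -3.59) | -7.49 (-7.73 to -7.24) |
| Raw mean | -3.72 | -7.42 |

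At both times the equal-weight interval excludes the subject-weighted mean. The SE ratio is 0.121/0.087 = 1.39 at 52 weeks and 0.172/0.124 = 1.39 at 104. The formula with the true slopes gives (0.154 - 0.5) x 2 = -0.69 at 52 weeks. This one dataset gave -3.76 - (-2.92) = -0.84, because its estimated group difference came out above 2.

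**The case against.** **The SAP does not say 50:50.** A reader might infer from the shell that equal weighting is specified. It is not. With use, prior study and region as class factors and time continuous, LS means come out by level of those factors. One overall AD row needs a contrast or an added one-level factor, whose weights the SAP leaves open. This stands: equal weighting is the default convention, not a stated rule.

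**The word pooled refers to prior treatment arms.** A reader might take it in SAP 8.1 as a commitment to average users and non-users by case mix. The text pools treatment allocation and says nothing about use. Only the single AD column implies an overall value. Figure 14.2.4.2 might split by use, but its layout is not shown.

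**The two MMSE tables would not reconcile anyway.** A reader might expect observed weights to bring Table 14.2.1.2 into line with the observed means in Table 14.2.1.1. They would not, because Table 14.2.1.1 takes the last value before first dose in this study as baseline and Table 14.2.1.2 takes the prior-study baseline.

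**The size depends on assumptions.** The illustrated shares all lie below 50%, which builds in a discrepancy. Any loss of coverage depends heavily on the number analysed, which the documents do not give. With an assumed slope SD of 3 points per year, a 20% non-user share and a 1-point gap, the equal-weight interval misses the subject-weighted mean in about 62-79% of trials for 800-1200 subjects, but 28% for 300. SAP 7.4 says MMSE collection began only with protocol version 3.0, so the smaller number cannot be excluded.

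**Little hangs on the result.** The study has no control arm, Protocol 9.1 names no efficacy endpoint, and Protocol 9.3.2 plans no inferential statistics. No decision uses this LS mean, and equal-weight standardisation is a recognised convention. This limits the importance of the point but does not supply the missing weights or the by-use rows.

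**Conclusion.** The point holds in a limited form. The model allows different slopes by AChEI/memantine use, yet the table reports one AD LS mean and CI per year, with no results by use and no weights. If the usual default is followed, the value describes an equal mix of users and non-users, of prior studies and of regions. It misdescribes the AD subjects unless use is near 50% or the groups do not differ.

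The documents cannot show whether a discrepancy would arise or how large it would be, because the share of users and the difference between groups are both absent. The illustrative range given above rests on the assumed 10-40% non-user share, a slope gap of 0.5-2 points per year and no main effect of use. The documents do not support saying that the SAP prescribes 50:50, or that the reported value is wrong by a known amount. This is a modest, inexpensive correction to a descriptive table.

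**What to change.** In SAP 8.1 and Table 14.2.1.2:

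1. Report annual LS means and 95% CIs separately for AChEI/memantine Yes and No.
2. If an overall AD row is kept, compute it as a contrast weighted by the proportions of use, prior study and region among the AD subjects analysed. Count each subject once. State the weights in the footnote.

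The cost is a short contrast statement and two extra rows or columns. The fitted model does not change and no new data are needed. Switching on an observed-margins option would not be enough. Applied to LS means by use, it reweights the other factors but still returns separate Yes and No rows. In a repeated-measures dataset it also counts records unless a subject-level dataset is supplied, so subjects followed longer would weigh more.

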### 8.2 EQ-5D-5L

The EQ-5D-5L is a standardized instrument developed by the EuroQol Group to describe and value health-related quality of life. The EQ-5D-5L will be performed at baseline and approximately every 6 months thereafter (or upon early termination). There will be two

applications of the self-reported EQ-5D-5L at each visit: one version will be completed by the subject and a second copy of this version will be completed by the caregiver.

The instrument comprises the following five dimensions: mobility, self-care, usual activities, pain/discomfort and anxiety/depression. Each dimension is rated by the subject and caregiver on a 5-point scale as having “no problems” (a score of “1”), “slight problems” (a score of “2”), “moderate problems” (a score of “3”), “severe problems” (a score of “4”), and “extreme problems” (a score of “5”) based on descriptive examples; the scores are not intended to be summed. Present overall state of health is also to be rated on a vertical visual analogue scale (approximately 20 cm in length) from 0 to 100 (the higher the number the better the quality of life). Each of the five dimensions as well as the overall state of health will be summarized descriptively by visit. Following the 24-Aug-2015 CRF migration, the original EQ-5D-5L eCRF was inactivated and the EQ-5D-5L Patient Rated and EQ-5D-5L Caregiver Rated eCRFs were activated. For subjects under version protocol version 1.1, only the EQ-5D-5L was applied to the subject, who should receive no help from the caregiver. For subjects under protocol version 2.1 or later versions, EQ-5D-5L is to be applied separately to both subject and caregiver. For the purposes of this summary, data obtained from the original EQ-5D-5L eCRF prior to the 24-Aug-2015 CRF migration and data obtained from the EQ-5D-5L Patient Rated eCRF after the 24-Aug-2015 CRF migration will be used.

The EQ-5D-5L health economic and economic modelling, and additional sensitivity analyses will be addressed in a separate external SAP.

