The majority of the safety assessments (described further in Section 7) will be repeated at each visit, *i.e.*, approximately 2 weeks post-Baseline and at visits occurring approximately every 3 months (13 weeks) relative to Baseline. These assessments include adverse event and concomitant medication recording, seated blood pressure and pulse, body weight, clinical laboratory testing (*e.g.*, hematology and serum chemistry panels), serum pregnancy testing in women of childbearing potential, and targeted physical and neurological examinations. The 12-lead ECGs will be obtained approximately every 6 months (26 weeks) relative to Baseline. Throughout the assessments for safety, the investigator is to be cognizant of the potential for serotonin toxicity, taking the MMSE into consideration as well.

The EQ-5D-5L, applied to the subject and to the caregiver on behalf of the subject, will be evaluated at Baseline (as it is not used in the Phase 3 studies of prior participation). The RUD-Lite will be also be evaluated at Baseline if not available from within the prior 42 days. These evaluations will be repeated approximately every 6 months (26 weeks) relative to Baseline.

The same aforementioned 13-week and 26-week schedules of in-clinic assessments will be maintained for continued treatment beyond the first 12 months (if there is re-consent at Visit 6), with no requirement for the Week 2 visit or Week 6 telephone contact in the second or any subsequent year of participation. Continued treatment will be restricted to those subjects for whom continued benefit is expected by the investigator to outweigh risk and informed consent is provided.

For subjects who do not re-enroll for a subsequent extension of treatment, identified end of treatment evaluations will be performed at the final on-treatment visit (*e.g.*, Visit 6). If a subject discontinues prematurely, an early termination visit should be conducted at which time all assessments identified for Visit 6 should be performed.

Post-treatment safety assessments will be conducted at a follow-up visit, to be scheduled to occur approximately 4 weeks after the last dose of study drug for all subjects who cease to take LMTM (regardless of the reason for discontinuation).

A schedule of assessments is shown in Table 4-1. Assessments are listed by visit in Appendix A: Assessments by Visit.

Table 4-1 Schedule of Assessments

Visit Name	Baseline ^a						First 12 Month Open-Label Extension ^b						Follow-up ^c

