9.2 Sample Size Calculations

Not applicable to this open-label extension study.

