9.3.3 Health Economic Analysis

A summary of the planned analyses is provided below; a detailed description of the planned analyses, as well as intended sensitivity analyses, will be provided in the SAP.

In order to investigate the pharmacoeconomic impact of LMTM, two approaches will be used:

- a cost consequence analysis (CCA), and
- a cost utility analysis (CUA).

With a cost consequence analysis, a broad set of relevant outcomes (here the primary and secondary outcomes) can be tabulated and discussed in relation to costs (Mauskopf *et al.*, 1998). Costs and outcomes are presented separately.

In the cost utility analysis, the incremental cost effectiveness ratio (ICER) is analyzed. As an outcome, the gained quality adjusted life years (QALY) derived from the EQ5D instrument will be used.

Both pharmacoeconomic approaches mentioned above include a risk of getting non-significant effects regarding costs, as clinical trials evaluating efficacy are typically

underpowered with respect to pharmacoeconomic results and long-term effects cannot be assessed due to time constraints in the clinical trials. Therefore, a modeling approach will complement the analysis.

9.3.3.1 *Resource Use*

The Resource Utilization in Dementia instrument (RUD) is a comprehensive and validated instrument collecting data on resource use in trials, with the aim to calculate costs from a societal viewpoint. The RUD Lite questionnaire, a short version of RUD mainly discarding the resource use by the caregivers, is employed in this study. All subjects for whom RUD Lite data was collected for at least one time point will be included in the summaries.

Together with costs of institutional care, the value of informal care is the heaviest cost driver in dementia care. Three components of caregiver time will be included in the analysis:

- time spent on toilet visits, eating, dressing, grooming, walking and bathing;
- time spent on shopping, food preparation, housekeeping, laundry, transportation, taking medication and managing financial matters; and
- time spent on supervising the subject.

Each component of caregiver time will be calculated as the hours of care on a typical day multiplied by days spent on providing these services. The caregiver time will be summarized for each treatment group by visit and with AChEI and/or memantine status at randomization, severity, and geographic region.

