#### 4.1 Conventions

The precision of original measurements will be maintained in summaries, when possible. Means, medians and standard deviations will be presented with an increased level of precision; means and medians will be presented to one more decimal place than the raw data, and the standard deviations will be presented to two more decimal places than the raw data.

---

 Mapped data consists of medical history, concomitant medication, and AE data obtained during the prior studies and imported into the 020 database (for handling of these data see Sections 5.5, 5.6, and 7.1, respectively).

Unless otherwise specified, summaries of continuous variables that have some values recorded using approximate values (e.g., < or >) will use imputed values. The approximate values will be imputed using the closest exact value for that measurement. For tables where rounding is required, rounding will be done to the nearest round-off unit. For example, if the round-off unit is the ones place (i.e., integers), values  $\geq XX.5$  will be rounded up to  $XX+1$  while values  $< XX.5$  will be rounded down to  $XX$ .

For percentages, unless they are calculated to be exactly 0% or 100%, values of very small or very large percentages will be reported as  $<0.1\%$  and  $>99.9\%$ .

For by-visit tables, percentages will be based on available data and denominators will generally exclude subjects with missing values. For frequency counts of categorical variables, categories whose counts are zero will be displayed for the sake of completeness. For example, if none of the subjects discontinue due to “lost to follow-up”, this reason will be included in the table with a count of 0.

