## List of Figures

Figure Number	Figure Description
14.2.4.1	Observed Mean MMSE by Visit (Safety Population)
14.2.4.2	Annualized Mean Change from Baseline in MMSE (Safety Population)
14.3.5.1.1	Box Plots of Hemoglobin by Visit – Conventional Units (Safety Population)
14.3.5.1.2	Box Plots of Hemoglobin Change from Baseline by Visit – Conventional Units (Safety Population)
14.3.5.1.3	Box Plots of Hemoglobin by Visit – SI Units (Safety Population)
14.3.5.1.4	Box Plots of Hemoglobin Change from Baseline by Visit – SI Units (Safety Population)
14.3.5.2.1	Box Plots of Reticulocytes by Visit – Conventional Units (Safety Population)
14.3.5.2.2	Box Plots of Reticulocytes Change from Baseline by Visit – Conventional Units (Safety Population)
14.3.5.2.3	Box Plots of Reticulocytes by Visit – SI Units (Safety Population)
14.3.5.2.4	Box Plots of Reticulocytes Change from Baseline by Visit – SI Units (Safety Population)
14.3.5.3.1	Box Plots of Neutrophils by Visit (Safety Population)
14.3.5.3.2	Box Plots of Neutrophils Change from Baseline by Visit (Safety Population)
14.3.5.4.1	Box Plots of Albumin by Visit – Conventional Units (Safety Population)
14.3.5.4.2	Box Plots of Albumin Change from Baseline by Visit – Conventional Units (Safety Population)
14.3.5.4.3	Box Plots of Albumin by Visit – SI Units (Safety Population)
14.3.3.4.4	Box Plots of Albumin Change from Baseline by Visit – SI Units (Safety Population)
14.3.5.5.1	Box Plots of ALT by Visit (Safety Population)
14.3.5.5.2	Box Plots of ALT Change from Baseline by Visit (Safety Population)
14.3.5.6.1	Box Plots of AST by Visit (Safety Population)
14.3.5.6.2	Box Plots of AST Change from Baseline by Visit (Safety Population)
14.3.5.7.1	Box Plots of Alkaline Phosphatase by Visit (Safety Population)
14.3.5.7.2	Box Plots of Alkaline Phosphatase Change from Baseline by Visit (Safety Population)

Figure Number	Figure Description
14.3.5.8.1	Box Plots of Total Bilirubin by Visit – Conventional Units (Safety Population)
14.3.5.8.2	Box Plots of Total Bilirubin Change from Baseline by Visit – Conventional Units (Safety Population)
14.3.5.8.3	Box Plots of Total Bilirubin by Visit – SI Units (Safety Population)
14.3.5.8.4	Box Plots of Total Bilirubin Change from Baseline by Visit – SI Units (Safety Population)
14.3.5.9.1	Box Plots of Direct Bilirubin by Visit – Conventional Units (Safety Population)

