**Table 14.2.3**  
**EQ-5D-5L**  
**Safety Population: Subjects with at Least One Post-Baseline EQ-5D-5L Questionnaire**

	Time Point	AD (N= )	bvFTD (N= )	All Subjects (N= )
Mobility	Baseline 	n=	n=	n=
	I have no problems in walking about	xx (xx.x%)	xx (xx.x%)	xx (xx.x%)
	I have slight problems in walking about	xx (xx.x%)	xx (xx.x%)	xx (xx.x%)
	I have moderate problems in walking about	xx (xx.x%)	xx (xx.x%)	xx (xx.x%)
	I have severe problems in walking about	xx (xx.x%)	xx (xx.x%)	xx (xx.x%)
	I am unable to walk about	xx (xx.x%)	xx (xx.x%)	xx (xx.x%)
	Week 26	n=	n=	n=
	I have no problems in walking about	xx (xx.x%)	xx (xx.x%)	xx (xx.x%)
	I have slight problems in walking about	xx (xx.x%)	xx (xx.x%)	xx (xx.x%)
	...	xx (xx.x%)	xx (xx.x%)	xx (xx.x%)
Self-care	Baseline 	n=	n=	n=
	I have no problems washing or dressing myself	xx (xx.x%)	xx (xx.x%)	xx (xx.x%)
	I have slight problems washing or dressing myself	xx (xx.x%)	xx (xx.x%)	xx (xx.x%)
	...	xx (xx.x%)	xx (xx.x%)	xx (xx.x%)
	Week 26			
	...			
	...			

 Baseline is defined as the last non-missing value prior to first dose of study drug.

Note: Following the 24-Aug-2015 CRF migration, the original EQ-5D-5L eCRF was inactivated and the EQ-5D-5L Patient Rated and EQ-5D-5L Caregiver Rated eCRFs were activated. For the purposes of this summary, data obtained from the original EQ-5D-5L eCRF prior to the 24-Aug-2015 CRF migration and data obtained from the EQ-5D-5L Patient Rated eCRF after the 24-Aug-2015 CRF migration are used.

path\t\_program.sas date time

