**Table 14.3.3.1.1.1**  
**Hematology Values and Changes from Baseline at All Visits – Conventional Units**  
**Safety Population**

Laboratory Parameter	Target Visit	AD (N= )	bvFTD (N= )	All Subjects (N= )
Hematocrit (%)	Baseline 			
	n	n	n	n
	Mean (SD)	xx.x (xx.xx)	xx.x (xx.xx)	xx.x (xx.xx)
	Median	xx.x	xx.x	xx.x
	Min, Max	xx, xx	xx, xx	xx, xx
	By-visit Baseline for Week 2 Visit 			
	N	n	n	n
	Mean (SD)	xx.x (xx.xx)	xx.x (xx.xx)	xx.x (xx.xx)
	Median	xx.x	xx.x	xx.x
	Min, Max	xx, xx	xx, xx	xx, xx
	Week 2			
	N	n	n	n
	Mean (SD)	xx.x (xx.xx)	xx.x (xx.xx)	xx.x (xx.xx)
	Median	xx.x	xx.x	xx.x
	Min, Max	xx, xx	xx, xx	xx, xx
	Change from Baseline to Week 2			
n	n	n	n	
Mean (SD)	xx.x (xx.xx)	xx.x (xx.xx)	xx.x (xx.xx)	
Median	xx.x	xx.x	xx.x	
Min, Max	xx, xx	xx, xx	xx, xx	
...				
Hemoglobin (g/dL)				
.				
.				

 Baseline is defined as the last non-missing value prior to first dose of study drug.

 By-visit Baseline is defined as the baseline assessments from subjects with a non-missing assessment at that visit.

path\t\_program.sas date time

*Programming note: Table will include all hematology parameters collected from Central Laboratory, and all target visits and for Last Available On-Treatment Value. Please see Appendix A for visit windows.*

*Programming Note: Repeat table for the tables listed below*

*Table 14.3.3.1.1.2 Hematology Values and Changes from Baseline at All Visits – Conventional Units – Non-AChEI/Memantine Users (Safety Population)*

- Table 14.3.3.1.2.1 Hematology Values and Changes from Baseline at All Visits – SI Units (Safety Population)*
- Table 14.3.3.1.2.2 Hematology Values and Changes from Baseline at All Visits – SI Units – Non-AChEI/Memantine Users (Safety Population)*

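### EQ-5D-5L levels and categorical RUD Lite items are summarised visit by visit with no matched Baseline, so a change in who remains can pass for stability or improvement

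*SAP*

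**What the plan says.** **Denominators.** SAP 4.1 sets the general rule: "For by-visit tables, percentages will be based on available data and denominators will generally exclude subjects with missing values".

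**EQ-5D-5L.** SAP 8.2 states: "Each of the five dimensions as well as the overall state of health will be summarized descriptively by visit". Protocol 9.6.6 likewise plans a descriptive summary by visit. Table 14.2.3 is headed "Safety Population: Subjects with at Least One Post-Baseline EQ-5D-5L Questionnaire". Its shell prints the percentage at each response level at Baseline, at Week 26 and so on, with an n for each visit. It has no change, shift or same-subject Baseline row. The layout for the visual analogue scale is not shown.

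**RUD Lite.** In Table 14.2.2 the three caregiver-time items carry a change-from-Baseline block. The categorical items (missed work, hospital admission, emergency care, doctor visits, nursing services, accommodation) show percentages per visit only. The accommodation block includes a question on permanent moves since the last visit, but that is a collected item, not a comparison with Baseline.

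**What the SAP does elsewhere.** The laboratory tables include an extra Baseline row for each visit: "By-visit Baseline is defined as the baseline assessments from subjects with a non-missing assessment at that visit" (Table 14.3.3.1.1.1). Table 14.3.4.5.2 cross-tabulates ECG interpretation at each visit against Baseline.

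**Who stays.** Protocol 4.4: "Continued treatment will be restricted to those subjects for whom continued benefit is expected by the investigator to outweigh risk". This is re-judged about every 12 months, first at Visit 6 (Week 52). Protocol 5.3 also lets the investigator stop treatment because the subject is worsening. It counts cognitive worsening under lack of efficacy, and it bars continuation in Germany and the Netherlands once a subject cannot consent.

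**The concern.** In a progressive disease with no control arm, a reader will compare the Baseline row with later rows. In these two layouts the rows describe different people: Baseline covers everyone with at least one post-Baseline form, and each later row covers those still attending. If subjects who are worse off leave more often, the percentage with problems falls, or rises less than it should, even when no individual improves. The reasons for leaving given in the protocol make that direction plausible. For the EQ-5D-5L levels and the RUD Lite categories, this SAP offers no paired summary to set against the impression.

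**Working it through.** The plan contains no figure to reproduce. Protocol 9.2 gives the sample size calculation as "Not applicable to this open-label extension study", and no retention rate is stated for the extension. The numbers below are illustrations.

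**Inputs**
- Available-data denominators: SAP 4.1.
- Share impaired at Baseline, p = 40% (10% for a rarer RUD Lite yes/no item): assumed.
- Retention of 60% and 80%: borrowed from the completion range that Protocol 4.2 assumes for the double-blind studies, not the extension. Values of 50% and 40% widen the range and are assumed.
- MMSE decline of 2 to 4 points per 12 months in Alzheimer's disease: Protocol 8.1. MMSE SD of 4 to 6 and the strength of selection: assumed.

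**Categorical items, nobody changes**

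Observed share at a later visit = p × r_imp / [p × r_imp + (1 − p) × r_oth], where r_imp and r_oth are the fractions retained among impaired and other subjects.

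| p | r_imp | r_oth | Calculation | Observed |
|---|---|---|---|---|
| 40% | 80% | 80% | 0.32 / 0.80 | 40.0% |
| 40% | 60% | 80% | 0.24 / 0.72 | 33.3% |
| 40% | 50% | 80% | 0.20 / 0.68 | 29.4% |
| 40% | 40% | 80% | 0.16 / 0.64 | 25.0% |
| 10% | 60% | 80% | 0.06 / 0.78 | 7.7% |
| 10% | 40% | 80% | 0.04 / 0.76 | 5.3% |

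The apparent improvement on the 40% item is 6.7, 10.6 or 15.0 points under unequal retention, and zero under equal retention. If impaired subjects stayed more often (80% against 60%), the share would rise to 0.32 / 0.68 = 47.1%, so the direction is also an assumption.

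**The same case with a By-visit Baseline.** Under 60%/80% retention, the retained subjects' own Baseline share is 0.24 / 0.72 = 33.3%. Set against the later 33.3%, the change is 0, which is correct.

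**Timing.** Both instruments are collected at Weeks 26 and 52 and about every 6 months after that. The yearly judgment follows the Week 52 assessments, so it affects Week 78 onward. Weeks 26 and 52 are affected only by other discontinuations.

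**MMSE, for comparison.** If a fraction r is retained and score correlates rho with retention, the mean of those attending is lifted by rho × SD × φ(z) / r, where z is the normal cut-off that retains r. With rho 0.3 to 0.7 and SD 4 to 6, the lift is 0.4 to 1.5 points at 80% retention and 0.8 to 2.7 at 60%. At 60% retention:
- hiding a 2-point decline needs rho of 0.52 to 0.78;
- hiding 3 points needs 0.78 to 0.93 at SD 5 to 6 and is impossible at SD 4;
- hiding 4 points is not achievable.

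A simulation (400,000 subjects, Baseline mean 18, retention selected on a noisy Week 52 score) gave the following for a true change of −3.0 points over 18 months, i.e. 2 per year:

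| Retained | Unpaired change in mean | Paired change |
|---|---|---|
| 80% | −1.7 | −2.8 |
| 60% | −0.6 | −2.7 |

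The curve of observed means is flattened, heavily so at the low end of decline with strong selection. Pairing recovers most of the true change but leaves a bias of about 0.15 to 0.3 points, because selection also acts on the course of change.

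**The case against.** **These are secondary, descriptive outputs.** The objectives are access and long-term safety, and efficacy endpoints are declared not applicable. The protocol itself asks for by-visit description. The shells print n per visit, discontinuations are tabulated by period and reason, and individual values are listed. This limits the stakes and makes attrition visible. It does not link attrition to these outcomes, so the row-to-row comparison stays uninterpretable.

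**Some leavers do contribute.** The early termination visit includes both instruments, and its values enter the analysis windows. This softens the effect at the visit of leaving, but the subject is absent from every later row. Deaths and consent withdrawals are exempt from that visit.

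**A separate SAP may cover it.** Additional EQ-5D-5L and RUD Lite sensitivity analyses are assigned to an external SAP that is not available here. It may help, but it does not alter tables specified in this one.

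**MMSE is already handled.** A reader might infer that the MMSE results share the defect, since Figure 14.2.4.1 plots observed means. The documents do not support that. The figure cites Table 14.2.1.1, which prints a paired change from Baseline, and SAP 8.1 adds a repeated-measures mixed model with annualised LS means, shown in Figure 14.2.4.2. At the protocol's rate of decline, attrition would flatten the curve rather than produce stability or improvement. The figure image is not reproduced, so its layout is known only from its title and source.

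**The RUD Lite population rule is not the cause.** Table 14.2.2 requires a post-Baseline form, whereas Protocol 9.3.3.1 states: "All subjects for whom RUD Lite data was collected for at least one time point will be included in the summaries". A reader might blame this for the bias. In fact it drops some early leavers from the Baseline row and so brings that row nearer to the later ones; restoring them would widen the unmatched gap. The discrepancy is real but separate.

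**Conclusion.** The point holds for Table 14.2.3 and for the categorical items of Table 14.2.2. Both report unpaired percentages of those available, and retention depends by design on worsening and, from Week 78 onward, on judged benefit. With 40% impaired at Baseline and no true change, the artefact is about 7 to 11 points at 60/80 and 50/80 retention, and nil if retention is equal.

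These sizes rest on assumed prevalence and retention. The documents do not show that retention will differ by severity, only that the rules make it plausible. It would also be too strong to infer that the yearly judgment distorts every visit, that all RUD Lite items are affected (caregiver time is paired), or that a matched Baseline would give an unbiased estimate of change. What remains is a modest, specific gap in presentation, and the SAP already contains the means to close it.

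**What to change.** 1. Add By-visit Baseline rows, as in Table 14.3.3.1.1.1, to Table 14.2.3 and to the categorical items of Table 14.2.2.
2. Add counts of better, same and worse than Baseline at each visit for each EQ-5D-5L dimension.
3. State in a footnote that pairing removes the shift in composition but not selection on the course of change.
4. For MMSE, at most show the Baseline mean of the same subjects at each visit of Figure 14.2.4.1, or refer the reader to the paired change in Table 14.2.1.1.
5. Separately, reconcile the RUD Lite population in Table 14.2.2 with Protocol 9.3.3.1, or record the departure in SAP section 9. This is a consistency correction, not a remedy for attrition.

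The cost is a small SAP revision and a few extra table rows. No new data are needed.
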